12.5.4 Confirmatory Analysis

No formal confirmatory analysis is foreseen in this study.

FEV₁, HDL-C, and WBC will be analyzed in the real scale. Other clinical risk endpoints, which will be analyzed in the logarithmic scale, will be back-transformed to provide relative effects.

The primary analysis for the “smokers’ health profile” endpoints will be based on a mixed model for repeated measurements (MMRM). The model will include the endpoint value as the dependent variable, product use pattern category, visit (V7, V10, and V16), and exposure by visit interaction as fixed effects, with adjustment for site, sex, and Baseline endpoint value. In order to adjust for potential residual confounding, covariates found to be not balanced between THS-use and CC-use will be included in the final model. Modeling assumptions will be evaluated and model fit assessed by the analysis of residuals (model diagnostics) and by comparing the values predicted versus the observed endpoint values (calibration).

The point and interval estimate of the contrast of THS-use versus CC-use at V16 will be tabulated for the FAS-EX.

Supportive analysis will be conducted on the FAS-AR and PP set.

The detailed analysis methods, including subgroup analyses, are given in the SAP.

Confidentiality Statement

Data and information contained in this document are considered to constitute trade secrets and confidential commercial information, and the legal protections provided to such trade secrets and confidential information are hereby claimed under the provisions of applicable law. No part of this document may be publicly disclosed without the written consent of Philip Morris Products S.A.

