**Table 3: Baseline Covariates for “Smokers’ Health Profile” Analysis**

Endpoint	Defined Covariates	Evaluated Covariates
FEV 1 %pred	Smoking intensity	Age  , Race/Ethnicity  , Height  , Diet, Exercise, BMI, Weight, Smoking duration
Total NNAL	Age, Smoking intensity	Other exposure

1 Listed covariates are defined as follows:

- Smoking intensity: average daily CC consumption measured by item 3 from the smoking history questions
- Smoking duration: measured by item 2 from the smoking history questions
- Age, Weight, Height, BMI : continuous variable
- Race/Ethnicity: (White Hispanic, White not Hispanic, Black or African American, Asian, Other) in substitution of the Caucasian origin variable if found significant between THS-use and CC-use product use exposure groups at JV4, V16[
- Diet, Alcohol intake, Exercise (total weekly time), sleep deficit, and Other exposure as collected in the Lifestyle questions

2 These variables are accounted for in the %predicted assessment. Race/Ethnicity will be included in the statistical model in place of Caucasian origin variable if found significant between THS-use and CC-use product use exposure groups at JV4, V16[.

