### 10.3 Per Protocol Population

The PP population is a subset of the FAS-EX and includes all randomized subjects who:

- Are subjects randomized to THS 2.2 who have a product use pattern category of THS-use or are subjects randomized to CC who have a product use pattern category of CC-use.
- Were included in the PP population in the original study.
- Do not make a quit attempt (see Section 6.3.3 “Adherence to Product Allocation”).
- Have no major protocol deviation that impacts the overall subject evaluability (see Section 11.1 “Major Protocol Deviations”).
- Have data for at least one endpoint of the “smoker’s health profile” which is not missing or excluded from the PP analysis at V7, V10, or V16, because of a major protocol deviation on product adherence and diary adherence (see Section 6.3.3 “Adherence to Product Allocation”) impacting evaluability (See Section 11.1 “Major Protocol Deviations”).

Subjects included in the PP population are analyzed as per randomized arm.

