## **12.3 Demographics and Other Baseline Characteristics**

The demographic variables and other baseline characteristics such as age, sex, race, body weight, height, BMI and waist circumference will be summarized by 6-month and 12-month

product use pattern categories for the FAS-EX, and stratified as described in Section 12.1.1 for the 12-month product use pattern categories. In addition, the analysis will be presented for the FAS-EX for only those subjects who enrolled into the extension study for both 6-month and 12-month product use pattern categories. Analysis will also be presented by randomization arm for the Safety and PP populations (Listing 15.3.1.7; Tables 15.2.1.4.1.\*, 15.2.1.4.2.\*). The summary will be produced also for the FAS-AR if it is different from the Safety population post-randomization. Other baseline characteristics will also be performed as described below.

There will be no inferential analyses of baseline characteristic data performed; however hypothesis testing will be conducted to assess baseline comparability of THS-use and CC-use product use exposure groups at ]V4, V10[ and ]V4, V16[ (for all the covariates in Table 3) for the FAS-EX by means of Analysis of Variance method and chi-square tests for continuous and categorical variables, respectively (Tables 15.2.1.4.3.1 and 15.2.1.4.3.2). These results will be considered for the analysis as described in Section 12.7.1.2 “Smokers’ Health Profile Endpoints Evaluation”.

Baseline comparability will also be conducted between subjects enrolled and not enrolled in the extension study among those who completed V10 (Table 15.2.1.4.4).

Subject responses, individual educational attainment, annual household income and composite classifications will be listed for the SES questionnaire (see Section 7.2.7 “Socio-Economic Status Questionnaire”). The number and percentage of subjects in each of the socio-economic status gradings will also be summarized (Listing 15.3.1.11; Tables 15.2.1.4.1.\*, 15.2.1.4.2.\*).

Subject response to items from the Prochaska questionnaire (see Section 7.2.4 “Prochaska ‘Stage of Change’ Questionnaire: Intention to Quit Smoking”) will be provided in listings and summary tables (Listing 15.3.1.4; Tables 15.2.1.4.1.\*, 15.2.1.4.2.\*).

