### 12.7.1.2 Smokers' Health Profile Endpoints Evaluation

The following endpoints of the “smokers’ health profile” values at Baseline, at V7, at V10, and at V16 will be log-transformed (basee) prior to the analysis: sICAM-1, 11-DTX-B2, 8-epi-PGF2 $\alpha$ , COHb, and Total NNAL. HDL-C, WBC, and FEV1 will be analyzed in the original scale. Concentration of urinary clinical risk endpoints and BoExp will be adjusted for creatinine, as defined in Section 7.1.1 “Clinical Risk Endpoints and Biomarkers of Exposure in Urine”.

Clinical risk endpoints will be analyzed in the FAS-EX population for the subgroup comparing THS-use with CC-use categories, using a MMRM adjusting for sex, Caucasian origin, visit, value of the endpoint at Baseline and its interaction with visit, product use pattern category and its interaction with visit, and other Baseline covariates relevant for each specific clinical risk endpoint. Site will be included as a random effect [20]. Additional Baseline characteristics are defined for each endpoint of the “smokers’ health profile” in Section 4.1.4 “Covariates for Smokers’ Health Profile Analysis” and summarized in Table 3. Model will include terms for the “Defined Covariates” and for the subset of “Evaluated Covariates” selected if found to be significant at 10% level (between THS-use and CC-use) at Baseline for at least one of the 6-month (same as original study) or the 12-month product use categories (Table 15.2.3.1).

Modeling assumptions are evaluated and model fit is assessed by the analysis of residuals (model diagnostics) and by comparing the values predicted versus the observed endpoint values (calibration).

The SAS code for the mixed model to be used is shown below:

```
Proc mixed data=_data_ method=reml maxiter=200;  
Class subject product_use site sex caucasian_origin visit;  
Model endpoint = baseline sex caucasian_origin product_use visit  
                  product_use*visit baseline*visit <covariates> / ddfm=kr;  
Random site;  
Repeated visit / subject=subject type=un r rcorr;  
Lsmeans product_use*visit / slice=visit alpha=0.05 diff cl pdiff;  
Run;
```

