### **12.7.1.3 Supportive Analysis**

#### **12.7.1.3.1 PP Analysis (Subjects Adherent to the Assigned Product)**

The primary analysis of the “smokers’ health profile” endpoints (see Section 12.7.1.2 “Smokers’ Health Profile Endpoints Evaluation”) will be repeated as a secondary analysis for the PP population (Table 15.2.3.2.2) using a 95% CI and 2-sided p-value. Subjects will be analyzed as randomized by means of a MMRM model including the same adjustment covariates used for the primary analysis (see Section 12.7.1.2 “Smokers’ Health Profile Endpoints Evaluation”), except that randomization arm will be used instead of product use category.

Forest plots of THS 2.2 versus CC arms will be displayed at V7, V10, and V16 for the PP population (Figure 15.1.1.2).

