#### **12.7.1.3.3 FAS-EX Supportive Analysis**

A supportive analysis will be conducted on the “smokers’ health profile” endpoints for the FAS-EX (Table 15.2.3.2.1) to compare the Dual-use versus CC-use at V7, V10, and V16. Subjects will be analyzed by means of a MMRM model including the same adjustment covariates used for the primary analysis (see Section 12.7.1.2 Smokers’ Health Profile

Endpoints Evaluation”). The estimates of the difference/percent reduction (and 2-sided p-values) will be presented together with 95% CI for Dual-use vs CC-use and also displayed as forest plots at V7, V10, and V16 (Figure 15.1.1.1) for the FAS-EX population.

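### In the non-randomized FAS-EX comparison, listed covariates enter only through a 10% baseline test of THS-use against CC-use: a minor weakness with a cheap fix

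*SAP*

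**What the plan says.** SAP 10.2 assigns FAS-EX subjects to groups by reported use after randomization. SAP 12.7.1.2 always adjusts for the baseline endpoint value and its interaction with visit, sex, Caucasian origin, visit and site (random). Table 3 adds Defined Covariates: smoking intensity for every endpoint, and age for every endpoint except FEV1 %pred.

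The Evaluated Covariates in Table 3 are conditional. SAP 12.7.1.2 says they are "selected if found to be significant at 10% level (between THS-use and CC-use) at Baseline", and one significant result in either the 6-month or the 12-month categories is enough. Protocol 12.5.4 has the same logic: "covariates found to be not balanced between THS-use and CC-use will be included in the final model".

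The screen is fed by SAP 12.3, where "hypothesis testing will be conducted to assess baseline comparability of THS-use and CC-use product use exposure groups". No corresponding test is planned for Dual-use. The Dual-use against CC-use analysis (SAP 12.7.1.3.3) nevertheless takes over the result: "Subjects will be analyzed by means of a MMRM model including the same adjustment covariates used for the primary analysis".

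Race/Ethnicity has its own rule in Table 3. Footnote 1 uses it "in substitution of the Caucasian origin variable if found significant between THS-use and CC-use product use exposure groups", and both footnotes name only the 12-month period. For FEV1, footnote 2 says of Age, Race/Ethnicity and Height: "These variables are accounted for in the %predicted assessment".

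**The concern.** Confounding needs a covariate that differs between groups and also predicts the endpoint. Table 3 settles the second condition in advance, by listing candidates per endpoint. The screen then replaces the size of the imbalance with its significance, which depends on sample size. A modest imbalance in a covariate that the sponsor considers relevant will usually stay out of the model.

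Two further gaps follow. Subjects who become dual users may differ from cigarette users in other ways than THS users do, and no test looks for this. For WBC and FEV1, two programmers could fit different primary models, depending on whether they follow SAP 12.7.1.2 or the Table 3 footnotes.

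At stake is some avoidable measured confounding in the week-52 FAS-EX estimates, mainly where the list is long. The distinct covariates affected are:
- HDL-C: five.
- FEV1: about four (diet, exercise, BMI or weight, smoking duration), leaving out the three in footnote 2.
- WBC: three.
- 8-epi-PGF2α: two, counting BMI and weight as one.
- The other four endpoints: one each.

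**Working it through.** **1. The plan's own figure.** SAP 8 gives 475 per arm, 60% of the THS arm in THS-use, 20% loss, 65% enrollment and an SD of 6.4 %pred. The 60% can be read in two ways:
- As a share of all randomized: 0.60 × 475 = 285 THS-use, against 0.80 × 475 = 380 CC-use.
- As a share of those left after loss: 0.60 × 380 = 228, against 380.

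Multiplying by 0.65 gives 185 against 247, or 148 against 247, at V16. The half-width is 1.96 × 6.4 × √(1/185 + 1/247) = 1.22 %pred, or 1.30 with 148. The probability that it is at most 1.5 exceeds 0.999 in both cases. On the harshest reading (0.40 × 475 × 0.65 ≈ 123 against 247) it is 0.985. The plan's claim of more than 90% is reproduced.

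**2. One 10% test.** For a true standardized difference d, the chance of selection is P(|Z + d/√(1/n₁ + 1/n₂)| > 1.645).

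| d | 285 vs 380 | 228 vs 380 |
|---|---|---|
| 0.10 | 0.358 | 0.328 |
| 0.20 | 0.818 | 0.771 |

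**3. The SAP's either-window rule.** By SAP 16.3.2 and Table 20, the 12-month THS-use and CC-use groups are nested within the 6-month ones. The two test statistics therefore correlate at √(fraction retained). With 75-95% retained (assumed):

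| d | selected, 285 vs 380 | selected, 228 vs 380 | missed |
|---|---|---|---|
| 0.10 | 0.386-0.408 | 0.356-0.378 | 59-64% |
| 0.20 | 0.835-0.842 | 0.791-0.800 | 16-21% |
| 0 | 0.118-0.142 | 0.118-0.142 | – |

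**4. Expected FEV1 bias, one covariate.** Bias = 6.4 × r × E[observed difference × not selected]. Here r is the partial correlation with FEV1 given the terms always in the model (assumed; not in the documents). With 90% retained and 2 million draws:

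| d | r = 0.1 | r = 0.2 | r = 0.3 |
|---|---|---|---|
| 0.10 | 0.019-0.021 | 0.039-0.041 | 0.058-0.062 |
| 0.20 | 0.008-0.011 | 0.016-0.021 | 0.024-0.032 |

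The bias is smaller at 0.20 SD because such a covariate is usually selected.

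**5. Four covariates at 0.10 SD, all in one direction** (4,000 replicates, compared with adjusting for all four). The bias is 0.083 %pred at r = 0.1 and 0.162-0.177 at r = 0.2. The SE is 1-6% larger and coverage is 94-95%. With mixed directions the result is within 0.01 of full adjustment.

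**6. Dual-use against CC-use.** A covariate balanced for THS-use against CC-use enters only 12-14% of the time (the d = 0 row), whatever its Dual-use imbalance. If it is omitted, the bias is r × 6.4 × d. For illustration only, 0.2 × 6.4 × 0.2 = 0.26 %pred.

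**7. Race/Ethnicity windows.** For a covariate at d = 0.10 with 90% retained, the 12-month-only rule selects 0.334 or 0.307 of the time, against 0.395 or 0.365 for either window. This is indicative only, since Race/Ethnicity has five categories, but the two texts can give different models.

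**8. Does another planned run use the full list?**
- The PP analysis (SAP 12.7.1.3.1) does not: "Subjects will be analyzed as randomized by means of a MMRM model including the same adjustment covariates used for the primary analysis". In the THS 2.2 arm it is also restricted to those who "Are subjects randomized to THS 2.2 who have a product use pattern category of THS-use".
- The FAS-AR and multiple-imputation runs (12.7.1.3.2, 12.7.1.3.6) reuse the set.
- The missing-use, extension-enrolled and LLOQ runs name no other.
- The propensity analysis (12.7.3.2) selects stepwise at 15.7%, and its outcome model takes the primary covariates.

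**The case against.** The screen is pre-specified, follows the protocol and is transparent. The comparability tests and the selected covariates each have a table (15.2.1.4.3.1, 15.2.1.4.3.2 and 15.2.3.1). Relevance to the endpoint was judged beforehand. The strongest predictors are always in the model, and larger imbalances are mostly caught. All this stands, and it is why the effect is small.

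The propensity analysis also addresses self-selected use. It draws on a wider pool of baseline variables, and SAP 16.2 cites it as support for interpretation. That is fair, but it compares randomized arms. It estimates a different contrast and does not correct the FAS-EX estimate. The same holds for FAS-AR.

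The Race/Ethnicity footnotes can be read as a specific rule overriding a general one, since Race/Ethnicity replaces a term already in the model. That reading is reasonable, but the SAP does not state it.

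Changing the main model late has a cost. The study team is unblinded to original-study data after that study's lock or SAP finalization, whichever comes last (SAP 6.3.2), and baseline outputs are run before lock (SAP 13.1). This is a good argument for accepting a named sensitivity analysis as the minimum.

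A reader might infer that the FAS-EX result is unreliable. One could suppose three covariates at r = 0.2, all just under the 10% threshold at 148 against 247 and all in one direction: 3 × 0.2 × 6.4 × 0.171 ≈ 0.66 %pred, 44% of the 1.5 margin. Nothing in the documents supports that combination.

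**Conclusion.** The point holds as a minor one. A modest imbalance in a listed covariate will more often than not go unadjusted. Dual-use against CC-use has no screen of its own, no planned run shows whether this matters, and the Race/Ethnicity rule is ambiguous for two endpoints.

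For FEV1 the expected bias is about 0.02-0.06 %pred per covariate at 0.10 SD and 0.01-0.03 at 0.20 SD. It reaches about 0.18 for four covariates acting together (r up to 0.2), against a half-width of 1.22-1.30. These sizes rest on assumed imbalances, correlations and retention. No figure can be given for HDL-C, which has the longest list, and the Dual-use figure is only an illustration.

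Three stronger readings are not supported:
- The ±1.5 %pred statement does not depend on covariate selection, and it reproduces.
- A single-test calculation gives slightly larger biases (up to about 0.07 and 0.04 %pred), but the general rule in SAP 12.7.1.2 accepts either window.
- The carry-over to the exposure and nicotine models (SAP 12.7.2.2 and 12.7.2.3) is one yes/no item, a smoker in the household.

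Full adjustment would still leave unmeasured confounding.

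**What to change.** - Fit the FAS-EX MMRM with the full Table 3 list for each endpoint, without a significance screen, for both THS-use and Dual-use against CC-use. Do this at least as a named sensitivity analysis. Preferably make it the main model and keep the 10%-selected model for continuity with the original study.
- Where BMI and weight are both listed, name BMI. Do not force Age or Height into the FEV1 %pred model.
- State one Race/Ethnicity rule, identically in SAP 12.7.1.2 and both Table 3 footnotes.
- Report the subjects lost to missing covariates per endpoint, and record the change in SAP Section 9.

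**Cost.** No new data are needed; the work is an SAP amendment and one extra table. Added degrees of freedom raise the SE by about 0.5-0.7% for five terms and 1.0-1.4% for ten.

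The MMRM needs complete data on all its terms (SAP 12.1.4), and exercise time is generally missing if either of its items is (SAP 7.2.9), so some subjects will drop out. The rate is not given. An assumed 5% loss takes the FEV1 half-width to at most 1.30/√0.95 = 1.34. Reaching 1.5 would need a loss of about 1 − (1.30/1.5)² = 24%, or 34% starting from 1.22. If the full list becomes the main model, V7 and V10 estimates may differ slightly from the original study's.

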### 12.1.4 Handling of Dropouts or Missing Data (including outside the limits of quantification)

For the values of biomarkers and risk markers:

- Missing data at Baseline will be considered as missing completely at random, and only subjects with complete data for all the terms in the mixed model for repeated measures (MMRM) will be included in the analysis. Summary tables will include all available values.
- Missing data at Baseline for the propensity score analysis will be handled as described in Section 12.7.3.2 “Exposure/Response and Effect of Dual-Use on Smokers’ Health Profile”.
- Missing data after randomization will be considered as missing at random, and handled by means of MMRM approach.
- If more than 10% of the FAS-EX analysis population have missing data at Baseline or V16 for at least one of the primary endpoints, a sensitivity analysis will be conducted by means of a multiple missing imputation approach.

For laboratory parameters:

- Values below the lower limit of quantification (LLOQ) will be imputed using LLOQ/2. For values above the upper limit of quantification (ULOQ), the ULOQ will be used for calculation and reporting in summary tables.
- The number of values below LLOQ or above ULOQ will be presented in each summary table. If 50% or more data are below LLOQ or above ULOQ, only the number (%) of value below LLOQ or above ULOQ will be reported in the summaries, together with minimum (if no value below LLOQ is present) and maximum (if no value above ULOQ are present) of the observed values.
- For calculation of parameters derived as a ratio of two components (creatinine-adjusted 24-hour urine endpoints, Apo B/Apo A1) if the denominator is below LLOQ then the ratio will not be calculated and will be tabulated as “Not Calculated” in descriptive summaries and excluded from the main analysis. A sensitivity analysis

will be produced by including derived values using half LLOQ values for the denominator of the impacted endpoint for the FAS-EX.

- Missing data at Baseline will not be imputed.

For daily product use data:

- Missing product use data will be handled as specified in Section 16.3 "Data Handling and Derivation of Product Use Pattern Categories" and Section 12.7.1.3.3 "FAS-EX Supportive Analysis".

For calculation of questionnaires' scores:

- For MCEQ, domain or subscale scores will be derived by averaging the individual non-missing item scores if at least 50% are non-missing, otherwise they will be set to missing.

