The least squares (LS) means and estimate of the difference along with its 95% CI and 2-sided p-value will be presented in tables for HDL-C, WBC, and FEV1 at V7, V10, and V16. For other clinical risk endpoints of the “smokers’ health profile”, results will be presented back transformed in the original scale as a ratio, as well as percent reduction relative to CC-use (i.e. 1 – THS-use:CC-use ratio) at V7, V10, and V16 (Table 15.2.3.1.1). THS-use vs CC-use will also displayed as forest plots at V7, V10, and V16 (Figure 15.1.1.1) for the FAS-EX population. In case of model convergence issues, this will be reported in the study report

and additional covariance structures will be investigated with the following order: heterogeneous compound symmetry (type=csh), heterogeneous toeplitz (type=toeph), heterogeneous autoregressive (1) (type=arh(1)), and variance components (type=vc).

As the smoking cessation effect will be estimated in the SA-SCR-01 study (NCT02432729), the analysis methods for the estimation of the preserved effect will be detailed in a separate analysis plan (cross-study analysis).

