In case of missing baseline data, the median of non-missing baseline values across all FAS-AR subjects in the THS 2.2 arm will be imputed for each continuous variable and the mode of non-missing baseline values across all FAS-AR subjects in the THS 2.2 arm will be imputed for each categorical variable.

The final model will be fit using the following SAS code. Goodness of fit diagnostics and discrimination ability of the fitted model based on the area of the receiver operating curve will be provided in statistical output listings.

```
proc logistic data = _THSarmData_ outmodel=_psmodel_ ;  
model product_use(event='THS-use') = <model terms> /  
clodds=wald lackfit outroc = ps_r ;
```

```
output out= ps_p XBETA=ps_xb STDXBETA= ps_sdxs PREDICTED =  
ps_pred;  
run;
```

The variables included in the final PS model together with the odds ratios and 95% CIs will be tabulated (Table 15.2.4.16). The fitted model is used to predict scores on both the THS 2.2 and CC arms, using the following SAS code:

```
proc logistic inmodel=_psmodel_;  
score data = _alldata_ out=_predData_;  
run;
```

In case of missing values in covariates included in the final PS model, the same imputation approach used for PS model fitting will be adopted. For the scoring of subjects in the CC arm, the median and mode values used for imputation will be derived only from subjects in the CC arm of FAS-AR. Histograms of the predicted PS scores will be presented by randomization arm (Figure 15.1.2.1) and individual PS scores will be reported in the statistical output listings.

The second step consists of a MMRM model analysis conducted on the FAS-AR with the model terms noted below (including the same adjustment covariates used for the primary analysis - see Section 12.7.1.2 “Smokers’ Health Profile Endpoints Evaluation”) and including the interaction of predicted PS values fit as a natural cubic spline with the randomization arm and the interaction of predicted PS values fit as a natural cubic spline with visit (Table 15.2.4.17). The THS 2.2 vs CC effect at V10 and V16 will be tabulated for PS levels equal to 100%, 75%, 50%, and 25% and displayed as a forest plot (Figure 15.1.2.2). A PS\*randomization arm interaction p-value (via the spline interaction) of 15.7% or less will be considered as indicative of a statistically significant THS effect based on the level of adherence to THS.

The SAS code for the mixed model to be used is shown below:

```

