Proc glimmix data=_data_ method=rspl maxopt=200;  
Class subject rand_arm site sex caucasian_origin visit;  
Effect spl = spline(P_THS-use / naturalcubic);  
Model endpoint = baseline sex caucasian_origin rand_arm spl  
visit baseline*visit rand_arm*visit visit*spl  
rand_arm*spl <covariates> / ddfm=kr;  
Nloptions technique=nrridg;  
Random site;  
random visit / subject=subject type=un residual;  
Lsmeans rand_arm*visit / at P_THS-use=xxx slice=visit  
alpha=0.05 diff cl pdiff;  
Run;
```

where P\_THS-use=xxx is set to the 1, 0.75, 0.5, 0.25 for each PS level. Note that ‘method=rspl’ is equivalent to using ‘method=reml’ with proc mixed. Also, ‘nloptions technique=nrridg’ solves the iterative optimization problem by means of a ridge-stabilized Newton-Raphson algorithm as used by proc mixed. In case of model convergence issues, this will be reported in the study report and additional covariance structures will be investigated with the following order: heterogeneous compound symmetry (type=csh), heterogeneous toeplitz (type=toeph), heterogeneous autoregressive (1) (type=arh(1)), and variance components (type=vc).

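### The SAP's covariance fallback lists end in type=vc, which treats a subject's V7, V10 and V16 values as independent; the last step should keep within-subject correlation (minor, and only if that step is reached)

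*SAP*

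**What the plan says.** The primary MMRM (SAP 12.7.1.2) starts with an unstructured visit covariance, "Repeated visit / subject=subject type=un r rcorr". Site is a random effect and there is no random subject effect. The fixed effects include baseline, baseline by visit, and product use by visit.

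If convergence fails, this is to be reported, and "additional covariance structures will be investigated with the following order: heterogeneous compound symmetry (type=csh), heterogeneous toeplitz (type=toeph"), then "heterogeneous autoregressive (1) (type=arh(1)), and variance components (type=vc").

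The same list appears for the cough model (12.7.2.5), the propensity model (12.7.3.2) and the multiple imputation analysis (12.7.1.3.6). Several secondary analyses adopt the 12.7.1.2 approach.

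SAP 12.1.4 states: "Missing data after randomization will be considered as missing at random, and handled by means of MMRM approach".

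In the propensity model the only within-subject covariance comes from "random visit / subject=subject type=un residual". The arm-by-spline term is not crossed with visit, and inference is model-based: "rand_arm*spl <covariates> / ddfm=kr". The decision rule is: "A PS\*randomization arm interaction p-value (via the spline interaction) of 15.7% or less will be considered as indicative of a statistically significant THS effect".

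**The concern.** With type=vc on a REPEATED statement, or on a residual RANDOM statement in GLIMMIX, the residual matrix is diagonal with one common variance. With no subject effect elsewhere in the model, a subject's three values are then independent given site and covariates. Two things follow.

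- **Primary contrast.** An MMRM handles missing-at-random data because a subject's V7 and V10 values inform the unseen V16 value through the covariance. Without that covariance, and with full product-use-by-visit and baseline-by-visit terms, the V16 contrast rests essentially on observed V16 values. SAP section 8 gives a 65% enrolment rate, so at least 35% of randomized subjects have no V16 value. Under SAP 16.3.2 those who do not enrol keep their 6-month category, so their V7 and V10 data are in FAS-EX to be used. Under vc they would add almost nothing at V16, and the primary result would nearly coincide with the enrolled-only sensitivity analysis in 12.7.1.3.5.
- **Propensity-by-arm test.** This term pools over visits. Under vc, two or three correlated values per subject count as separate subjects, and the standard error is too small even with no missing data.

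**Working it through.** **The plan's own figure.** The SAP ties 15.7% to the Akaike criterion: P(chi-square, 1 df, > 2) = 0.1573. It reproduces.

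**The gap in the list.** Covariance parameters for three visits: un 6, toeph 5 (three variances, two lags), csh 4, arh(1) 4, vc 1. Homogeneous compound symmetry (cs) has 2 and keeps the correlation. The list passes over it.

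**Residual correlation (assumption).** The documents give no within-subject correlation. Take compound symmetry with rho = 0.3, 0.5 or 0.7 across baseline, V7, V10 and V16. After adjustment for baseline the residual correlation is (rho - rho²)/(1 - rho²) = rho/(1 + rho), which gives 0.231, 0.333 and 0.412.

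**Propensity-by-arm test under vc.** With 65% of subjects having three visits and 35% having two, and residual correlation r, the design effect is:

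DE = 1 + r × (0.65×3×2 + 0.35×2×1)/(0.65×3 + 0.35×2) = 1 + r × 4.6/2.65

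This gives 1.40, 1.58 and 1.71. For a 2 df test (an assumption about the spline), the true level at a nominal 0.157 is 0.157^(1/DE):

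| rho | r | DE | true level |
|---|---|---|---|
| 0.3 | 0.231 | 1.40 | 27% |
| 0.5 | 0.333 | 1.58 | 31% |
| 0.7 | 0.412 | 1.71 | 34% |

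Simulation with the unstructured covariance kept gave 14-16%, so the specified model holds its level.

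**Primary V16 contrast under vc.** Inputs from SAP section 8: 475 per arm, 20% lost, 60% THS-use. This gives 475×0.8×0.6 = 228 THS-use and 475×0.8 = 380 CC-use subjects. Assume 65% of them are observed at V16, with no true effect. Non-enrolment depends on the V10 value in the THS-use group only, with logit slope 0.5 or 1.0 per SD. Under vc the model reduces to a separate regression at each visit with a pooled residual variance. With 1,500 runs, the simulation error at a 10% rate is √(0.1×0.9/1500) = 0.8 points.

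| Model | Slope 0.5 | Slope 1.0 | Largest bias |
|---|---|---|---|
| Baseline terms left out | 12% (7-20%) | 31% (13-51%) | 0.21 SD |
| Baseline and baseline by visit, as in the SAP | 7% (6-10%) | about 12% (10-12%) | about 0.07 SD |

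The figures are false-positive rates at nominal 5% for rho 0.5, with the range over rho 0.3-0.7 in brackets. The second row is the one that applies. If missingness is unrelated to V10, or related to it equally in both groups, and variances are equal across visits, the rate stays near 5% and the bias is about zero.

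If the SAP's 6.4 %pred is taken as the SD for FEV1, 0.07 SD is 0.07×6.4 = 0.45 %pred, or 0.45/1.5 = 30% of the planned ±1.5 margin.

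**The case against.** A reader might infer that the planned missing-data handling fails and that the propensity test rejects far too often as a matter of course. The documents do not support this. The specified model is unstructured and sound. The harm needs un, csh, toeph and arh(1) all to fail, which is unlikely for a Gaussian model with three visits and several hundred subjects. It is more plausible for the GLIMMIX models.

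A reader might also take a V16 bias of 0.2 SD or a false-positive rate above 30% as the size. Those figures leave out the baseline and baseline-by-visit terms, which the SAP keeps under every covariance structure. Larger figures need a residual correlation of 0.5 or more after baseline adjustment, for which the documents give no basis.

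The SAP also has a backstop. Multiple imputation (12.7.1.3.6) runs for any primary endpoint with more than 10% missing at baseline or Month 12. At about 35% missing it would run. It imputes from baseline, Month 3 and Month 6 values, which is the information that vc discards. This stands, with limits: it is a sensitivity analysis, it does not replace the primary estimate, and it does not cover the propensity or cough models.

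Finally, the propensity test is exploratory, the study has no formal hypotheses, and p-values were dropped for cough. That lowers the stakes. The 15.7% rule is still a stated criterion, and 12.7.1.3.2 uses the propensity analysis to interpret the FAS-AR result. Reporting non-convergence does not correct an estimate made under vc.

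**Conclusion.** Wrong as written, minor and conditional. In all three models the last fallback removes the within-subject correlation, which contradicts the missing-at-random handling in SAP 12.1.4.

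If it is reached, two consequences follow under the assumptions above:

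- **V16 contrast:** a false-positive rate of about 6-12% and a bias of up to about 0.07 SD. This needs V10-dependent non-enrolment that differs between the groups. Without that, and with equal variances across visits, the rate stays near 5%.
- **Propensity-by-arm test:** a rejection rate of about 27-34% at the stated 15.7% level (2 df). This needs only within-subject correlation, not any particular missingness.

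The sizes depend on the assumed correlation and missingness slopes. The inflation of the pooled test does not depend on the slopes, and positive correlation always pushes it upward.

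**What to change.** - In SAP 12.7.1.2, 12.7.2.5 and 12.7.3.2, replace the last fallback, type=vc, with homogeneous compound symmetry (type=cs). In the Gaussian models a random subject intercept is equivalent when the correlation is positive. In the logistic cough model the residual cs form is preferable, because a random subject intercept would change what the odds ratio means.
- In SAP 12.7.1.3.6, delete the covariance list. Each model there has one value per subject, so there is no repeated-measures covariance to choose.
- Do not add a general requirement for sandwich standard errors. The site effect is coded without a SUBJECT= option, so subjects who share a site are not independent blocks. A valid sandwich would have to cluster on site, and these documents do not state the number of sites. It would also leave the missing-data bias in place.

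The cost is wording in four places, with no new data or procedures.
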